#### 6.8.2 Prohibited concomitant medications

Section 10.6 presents a comprehensive (but not exhaustive) list of prohibited concomitant medications (recently approved drugs may not be included in the list and should be checked on a case-by-case basis). The Medical Monitor should be contacted if there are any questions regarding concomitant or prior therapy.

10 MAY 2023 Page: 39 of 97

#### **6.8.3** Other Treatment Considerations

Based on preclinical data, an increase in exposure of drugs that are sensitive substrates of OATP1B1/1B3, P-glycoprotein or breast cancer resistance protein (BCRP) during co-administration of elinzanetant due to inhibition of those transporters by elinzanetant could not be excluded. Results from a clinical drug-drug interaction study with the BCRP and OATP1B1/B3 substrate rosuvastatin showed no clinically relevant effect on the pharmacokinetics of rosuvastatin when administered together with elinzanetant. Therefore, medications that are substrates of BCRP and/or OATP1B1/1B3 can be administered together with elinzanetant without restrictions. Results from a clinical drug-drug interaction study with the sensitive P-gp substrate dabigatran etexilate (study 22081) showed no clinically relevant interaction. Therefore, medications that are substrates of P-gp can be administered together with elinzanetant without restrictions.

# 7. Discontinuation of Study Intervention and Participant Discontinuation/Withdrawal

# 7.1 Discontinuation of Study Intervention

It may be necessary for a participant to permanently discontinue study intervention. If study intervention is permanently discontinued, and if the investigator considers it medically justified, the participant may remain in the study without receiving the study intervention. As a general rule, all procedures scheduled for the end-of-treatment visit should be performed at the time of premature discontinuation of study intervention and documented. In case this is considered not medically appropriate for certain procedures (e.g. for invasive procedures if only short time has elapsed since the last scheduled assessment) this should be documented by the investigator. All scheduled study visits and procedures, except for study intervention, should continue if agreed by the participant. PK sampling is also not required. For participants who agree to continue in the study, any medication used after discontinuation of study intervention must be documented.

Treatment extension (part C):

Participants who prematurely discontinue from treatment during part C are asked to return to the EoT part C and FU part C visit.

For withdrawal from study see Section 7.2.

# 7.1.1 Pregnancy

The participants must discontinue study intervention in case of pregnancy (See Section 8.3.5).

## 7.1.2 Liver Chemistry Stopping Criteria

Discontinuation of study intervention for abnormal liver tests is required by the investigator when a participant meets one of the conditions outlined in Section 10.5 or in the presence of abnormal liver chemistries not meeting protocol-specified stopping rules if the investigator believes that it is in best interest of the participant. See Section 10.5 for further details.

No lab samples are taken during part C. In case the participant meets one of these thresholds in lab samples taken outside of the study these criteria apply.

10 MAY 2023 Page: 40 of 97

# 7.1.3 Platelet count Stopping Criteria

In the case of platelet counts below 50,000/mm^3, study intervention must be discontinued immediately.

In the case of platelet counts between 50,000/mm^3 and 75,000/mm^3, a retest should be performed within 72 hours of the initial test results. If values do not normalize within 7 days, study intervention must be discontinued.

No lab samples are taken during part C. In case the participant meets one of these thresholds in lab samples taken outside of the study these criteria apply.

# 7.1.4 Temporary Discontinuation

In the event that a participant experiences an AE which the investigator believes is treatment related and which the participant finds intolerable, a break in dosing of up to one week is permitted. If, on reintroduction of the study medication, the AE recurs and remains intolerable, the study drug will be permanently withdrawn. A break in dosing will not result in extension of the overall dosing period.

Temporary discontinuation is also allowed in the following two cases:

- Temporary discontinuation of study intervention for an intercurrent illness, at the discretion of the investigator.
- In the event of a trial-continuity issue (e.g. caused by a pandemic), the sponsor may provide additional guidance in study-specific communication.

# 7.1.5 Rechallenge

Study intervention may be restarted after a temporary interruption if deemed clinically appropriate by the investigator in collaboration with the Sponsor's representative (e.g. medical monitor).

# 7.1.5.1 Study Intervention Restart or Rechallenge After Liver Stopping Criteria Met

Section 7.1.5.1 is not applicable for the treatment extension (part C).

Study intervention restart or rechallenge after liver chemistry stopping criteria are met by any participant in this study is not allowed.

10 MAY 2023 Page: 41 of 97

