## 10.5 Appendix 5: Liver Safety Actions and Follow-up Assessments

## 10.5.1 Liver safety -related monitoring and discontinuation criteria

Investigators and participants should pay special attention to non-specific symptoms which may be associated with liver dysfunction; including anorexia, nausea, fatigue, right upper abdominal discomfort, vomiting, malaise, jaundice, fever, and rash.

10 MAY 2023 Page: 81 of 97

- Information on these symptoms should be asked for in case of abnormal liver laboratory values (Table 10-2) or any other suspicion of liver dysfunction.
- Participants should be regularly reminded to contact the investigator immediately if they are concerned about such symptoms, and unscheduled visits for evaluation should be considered
- In the case of increased liver values as defined in Table 10-2, a retest should be performed within 72 hours of the initial test results. If the abnormal liver values are confirmed in the retest, liver safety monitoring should be initiated.

Table 10-2: Liver Safety-Related Monitoring and Discontinuation Criteria

Lab result	Measures
ALT or AST > 3 x ULN	Initiate close observation as defined in Section 10.5.2.
AP > 2 x ULN b	Consider withdrawal of study intervention if the participant does not adhere to procedures required for close observation a Initiate close observation as defined in Section 10.5.2. Consider withdrawal of study intervention if the participant does not adhere to procedures required for close observation
ALT or AST > 3 x ULN and TBL > 2 x ULN	Withdraw study intervention and initiate close observation as defined in Section 10.5.2.
ALT or AST > 3 x ULN and INR > 1.5 x ULN	Withdraw study intervention and initiate close observation as defined in Section 10.5.2.
ALT or AST > 3 ULN with appearance of fatigue, nausea, vomiting, right upper abdominal quadrant pain or tenderness, fever, rash and/or eosinophilia (>5%)	Withdraw study intervention and initiate close observation as defined in Section 10.5.2.
ALT or AST > 5 x ULN for more than 2 weeks ALT or AST > 8 x ULN	Withdraw study intervention and initiate close observation as defined in Section 10.5.2. Withdraw study intervention and initiate close observation as
ALI OF A OLIV	defined in Section 10.5.2.

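### Section 7.1.5.1 lifts the ban on rechallenge after a liver stop for Part C, although Section 7.1.2 keeps the liver stopping criteria in force there

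*Protocol*

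**What the plan says.** Protocol Section 7.1.5.1 consists of two sentences. The first is the exemption: "Section 7.1.5.1 is not applicable for the treatment extension (part C"). The second is the rule: "Study intervention restart or rechallenge after liver chemistry stopping criteria are met by any participant in this study is not allowed".

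Section 7.1.2 requires the investigator to discontinue study drug when a Section 10.5 liver condition is met. It notes that Part C has no laboratory sampling and then adds: "In case the participant meets one of these thresholds in lab samples taken outside of the study these criteria apply". Section 7.1.3 treats platelets the same way: it says "No lab samples are taken during part C" and likewise keeps its thresholds in force for outside samples.

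The neighbouring sections that bear on restart are:

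- Section 7.1, on Part C: "Participants who prematurely discontinue from treatment during part C are asked to return to the EoT part C and FU part C visit".
- Section 7.1.4, which allows a break of up to one week for an intolerable treatment-related adverse event, followed by reintroduction. It then says "Temporary discontinuation is also allowed in the following two cases", namely an intercurrent illness (at the investigator's discretion) and a trial-continuity problem.
- Section 7.1.5: "Study intervention may be restarted after a temporary interruption if deemed clinically appropriate by the investigator in collaboration with" the sponsor's representative.
- Table 10-2 in Section 10.5.1, for each liver stopping criterion: "Withdraw study intervention and initiate close observation as defined in Section 10.5.2".

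**The concern.** The exemption and Section 7.1.2 pull in opposite directions. One foresees a liver stop in Part C and enforces it. The other withdraws, for that same part, the statement of what may not follow. Because the ban is the only rule in Section 7.1.5.1, the exemption can refer to nothing else.

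At stake is re-exposure after a possible drug-induced liver injury. Table 2-1 lists increased liver enzymes as a potential risk and names regular liver monitoring, close observation and stopping criteria as the mitigation. Section 8.3.6 makes any condition that triggers close liver observation an adverse event of special interest. In Part C the scheduled monitoring is absent, so more rests on the stopping rule and on what happens after it.

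**Working it through.** The point is textual and no figure in the plan needs reproducing. The check has three steps.

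**1. Can a liver stop occur in Part C?** Yes. Section 7.1.2 says the criteria apply to outside samples.

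**2. Does any text other than 7.1.5.1 bar restart after such a stop?**

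| Section | What it does in Part C | Bars restart? |
|---|---|---|
| 7.1.2 | Requires discontinuation | Silent on restart |
| Table 10-2 | Says to withdraw study drug | Silent on restart |
| 7.1 | Sends early discontinuers to the EoT and FU Part C visits | Implied only |
| 7.1.4 | Does not list a liver stop among temporary breaks | Implied only |
| 7.1.5 | Allows restart after a temporary interruption, with the sponsor's representative | No liver or Part C exception |
| 7.1.5.1 | Explicit ban | Switched off |

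The stop wording in 7.1.2 and Table 10-2 also governs Parts A and B, where the protocol still adds an explicit ban. It was evidently not thought sufficient alone.

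There is a route by which the gap could matter. Table 10-2 includes a stop for ALT or AST above 3 × ULN with symptoms, and Section 10.5.2 requires findings that lead to close observation to be reported as adverse events. An investigator could treat such an event as an intolerable adverse event or an intercurrent illness under 7.1.4 and look to 7.1.5 for restart. In Parts A and B, 7.1.5.1 blocks this. In Part C it does not.

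**3. What scheduled testing stands behind the rule?** The inputs are the safety blood sample row of Table 1-2 and the visits and rows of Table 1-3.

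- Parts A and B, on treatment after baseline: T2, T4, T6, T7, T9, T11 and T13 (Weeks 4, 8, 12, 16, 26, 36 and 52) = 7 samples in 52 weeks.
- Part C length: 156 − 52 = 104 weeks. Safety blood samples in Table 1-3: 0.
- Gaps between on-treatment Part C visits: 82 − 58 = 24, 107 − 82 = 25, 131 − 107 = 24 and 156 − 131 = 25 weeks.

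These counts describe the setting. They do not measure how often the gap would be met.

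**The case against.** The strongest reply is that the protocol already closes the route. Discontinuation is mandatory under 7.1.2, and Table 10-2 says to withdraw. Restart under 7.1.5 covers only temporary interruptions and involves the sponsor's representative. A Part C discontinuer goes to the EoT Part C visit, where Table 1-3 shows drug collected and none dispensed. On this view only a confirmatory sentence is missing, probably through a drafting slip prompted by the absence of Part C laboratory samples. The monitoring counts also belong to a different question, and the proposed wording would change none of them. Finally, once a threshold is detected, Section 10.5.2 requires close observation with sampling 2 to 3 times a week and does not exempt Part C.

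Much of this stands. Permanent discontinuation is the likely intent, no text expressly permits rechallenge, and the counts do not quantify the problem.

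Three things remain. First, none of those provisions bars restart in terms, and a rule disapplied for a named part can be read as deliberate. Second, the lack of study samples does not explain the exemption, because 7.1.2 and 7.1.3 meet the same circumstance by keeping their criteria active. Third, close observation is time-limited. Under Section 10.5.2 it can end after two consecutive normal or baseline liver enzyme results, once the work-up is available. If the drug were then restarted, no scheduled study test would pick up a recurrence.

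**Conclusion.** The concern holds. As written, the protocol keeps the liver stop in Part C, removes the only explicit ban on restarting after it, and gives no reason in that section. This is a contradiction on a hepatic safety rule that should be corrected, though not a reversal of the rule.

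The number of participants affected is expected to be small. It cannot be estimated, because the documents give no rate of liver stops detected in outside samples. The Week 4 and Week 12 efficacy analyses are unaffected. The conclusion rests on the current wording of Sections 7.1 to 7.1.5.1 and 10.5 and needs no numerical assumption.

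**What to change.** Delete the first sentence of Section 7.1.5.1. Alternatively, replace it with: *In Part C this rule applies whenever liver stopping criteria are met in a sample taken outside the study.* This brings the section into line with 7.1.2 and 7.1.3. If the sponsor does intend to allow rechallenge in Part C, the protocol should say so and justify it.

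The cost is one sentence in a protocol amendment, with no added visit, sample or procedure.

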# 7.2 Participant Discontinuation/Withdrawal from the Study

- A participant may withdraw from the study at any time at her own request, or may be withdrawn at any time at the discretion of the investigator for safety, behavioral, or compliance reasons.
  - O If a participant is tested positive for SARS-CoV-2 infection while on study, the investigator will have to decide whether staying in the study is compatible with participant and site personnel safety and wellbeing. In most cases, temporary discontinuation (see section 7.1.4) may be an appropriate solution. The decision should also take into account possible interaction between the study intervention and potential treatment for SARS-CoV-2 infection.
  - o If a participant discontinues treatment with tamoxifen/aromatase inhibitors in the main study (part A+B), the investigator will decide whether the participant should be withdrawn from the study.
    - If a participant discontinues treatment with tamoxifen/aromatase inhibitors during treatment extension (part C), she should be withdrawn from the study.
- At the time of discontinuing from the study, if possible, End of Treatment visit (either EoT or EoT part C visit) procedures should be conducted, followed by a FU visit as shown in the SoA and in particular described in footnote a) in Table 1-2.
  - Participants who have been randomized but not yet started study intervention do not need to undergo further study procedures other than return of supplies, before their study participation terminates.
  - o For withdrawal during the follow-up period, the participant should undergo the assessments scheduled for the next visit (FU Visit).
- The participant will be permanently discontinued both from the study intervention and from the study at that time.
- If the participant withdraws consent for disclosure of future information, the sponsor may retain and continue to use any data collected before such a withdrawal of consent.

For withdrawal from study intervention see Section 7.1.

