#### **Estimands**

The attributes of the main estimand for the primary endpoints are as following:

- Population: women aged 18-70 with VMS caused by adjuvant endocrine therapy, as described by the inclusion/exclusion criteria detailed in the protocol.
- Variable: Efficacy will be assessed based on 2 primary endpoints as listed below:
  - o Change in frequency of moderate to severe HFs from baseline to Week 4
  - o Change in frequency of moderate to severe HFs from baseline to Week 12.
- Treatment: 120 mg elinzanetant, placebo
- ICEs: see Table 3-2

Table 3-2: Primary Estimand: ICEs and Strategies to Address Them

107.0		o c	
ICEs a		Strategy	Data handling method
Temporary Treatment interruption b	AEs (treatment related/unrelated)	Treatment policy	Utilise the collected data after ICE.
	COVID-19 and administrative reasons	Treatment policy	Utilise the collected data after ICE.
Permanent discontinuation of randomized treatment	AEs (treatment related/unrelated) or Lack of efficacy		
	
 
For participants who remained untreated/on background therapy.
 
	Treatment policy	Utilise the collected data after ICE.
	
 
For participants who initiate alternative VMS treatment
 
	Treatment policy	Utilise the collected data after ICE.
	Other treatment- unrelated reasons, including COVID-19	Treatment policy	Utilise the collected data after ICE.
Intake of prohibited concomitant medication having impact on efficacy	All reasons	Treatment policy	Utilise the collected data after ICE.
Interruption/ discontinuation in intake of adjuvant endocrine therapy c	All reasons	Treatment policy	Utilise the collected data after ICE.

AE = Adverse event, COVID-19 = Coronavirus disease of 2019, ICE = Intercurrent event, VMS = Vasomotor symptoms

a) ICEs will be reviewed at the Blinded Review Meeting prior to the study unblinding

10 MAY 2023 Page: 24 of 97

Table 3-2: Primary Estimand: ICEs and Strategies to Address Them

1020 Redomini 102 Charegy Bata haraming metrica	ICEs a	Reason for ICE	Strategy	Data handling method
---	-------------------	----------------	----------	----------------------

b) Definition of temporary treatment interruption:

Week 1 = Treatment taken on <5/7 days during week 1.

Week 4= Treatment taken <80% during weeks 1-4 OR treatment taken on <5/7 days during either Week 3 or 4.

Week 12= Treatment taken <80% during weeks 1-12 OR treatment taken on <5/7 days during either Week 11 or 12.

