c) Definition of interruption/discontinuation in intake of adjuvant endocrine therapy:

For participants using tamoxifen: reduction of at least 50% of planned daily dosage taken during weeks 3 and 4 OR weeks 11 and 12 compared to baseline

For participants using aromatase inhibitor: reduction of at least 30% of planned daily dosage taken during weeks 3 and 4 OR weeks 11 and 12 compared to baseline

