	μ is the intercept,
	β is the baseline covariate effect (baseline coefficient),
	x_i is the baseline frequency HF for subject i ,
	t_k is the fixed effect of treatment k (k = $Elinzanetant$, $placebo$),
	p_m is the fixed effect of type of treatment m at baseline $(m=Tamoxifen, Aromatase inhibitor)$
	v_j is the fixed effect of Week j ($j=1, 4, 8 & 12$),
	$(tv)_{jk}$ is the interaction effect of treatment k by Week j ,
	α is the covariate effect for the interaction (xv)
	$(xv)_{ij}$ is the interaction effect of baseline frequency HF of subject i by Week j ,

version 3.0 Page: 31 of 87

PROC MIXED data=DATA; CLASS subject treatment week pretreatment; MODEL change = baseline treatment week pretreatment treatment*week baseline*week /ddfm=KR outp=resid s; REPEATED week / subject=subject type=un; RANDOM subject; /* only if AR(1) covariance structure is used */ LSMEANS treatment*week /cl diff; ESTIMATE 'Elinzanetant - Placebo at Week 4' treatment 1 -1 treatment*week 0 1 0 0 0 -1 0 0 /cl; ESTIMATE 'Elinzanetant - Placebo at Week 12' treatment 1 -1 treatment*week 0 0 0 1 0 0 0 -1 /cl;		$s_i \sim \text{Normal } (0, \sigma_s^2) \text{ is the random effect of subject } i \text{ (only if } AR(1) \text{ covariance structure is used),}$ $\varepsilon_{ijklm} \sim \text{Normal } (0, \sigma^2) \text{ represents the residual variance component with corr } (\varepsilon_{ij}, \varepsilon_{ij}) = \rho_{jj}, j \neq j'.$
ODS OUTPUT TESTS3=TYPE3 LSMeans=LSMEAN ESTIMATES=ESTIM;	SAS code:	CLASS subject treatment week pretreatment; MODEL change = baseline treatment week pretreatment treatment*week baseline*week /ddfm=KR outp=resid s; REPEATED week / subject=subject type=un; RANDOM subject; /* only if AR(1) covariance structure is used */ LSMEANS treatment*week /cl diff; ESTIMATE 'Elinzanetant - Placebo at Week 4' treatment 1 -1 treatment*week 0 1 0 0 0 -1 0 0 /cl; ESTIMATE 'Elinzanetant - Placebo at Week 12' treatment 1 -1 treatment*week 0 0 0 1 0 0 0 -1 /cl;

A treatment policy strategy will be applied to handle all of the ICEs in this trial in the main estimand. According to this strategy, all collected data should be utilized in the analysis irrespective of occurrence of the ICEs.

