Although all study participants are expected to be followed after ICEs, some missing data may occur. Missing values that occur while participants continue on their randomized treatment and simply represent missed assessments will be assumed missing at random (MAR). Such missing values could be intermittent or monotone and will be imputed using a Monte Carlo Markov Chain (MCMC) multiple imputation (MI) method. For the baseline value to be imputed, at least 2 post-baseline values out of the 4 post-baseline values (i.e., Week 1, 4, 8 & 12) need to be available. Possible missing baseline values will be imputed together with other intermittent missing values. Absolute values will be used for imputation steps.

Due to study design it will be difficult to implement a modelling approach aligned with the treatment policy strategy with the imputation model estimated from participants who discontinue the randomized treatment and provide data. The number of such participants is expected to be too small for estimating a robust imputation model. Therefore, the washout method will be used to impute missing data from participants who experience the ICEs (i.e. permanent treatment discontinuation) (Wang et al. 2023).

A placebo-effect is expected to be seen with the placebo group while the elinzanetant treatment effect will consist of both the placebo-effect and the effect of elinzanetant. The washout method effectively 'washes out' any pre-ICE treatment effect of elinzanetant in participants with an ICE randomized to elinzanetant, while modeling the mean placebo effect. Missing data in participants randomized to placebo will be assumed MAR.

version 3.0 Page: 32 of 87

For participants randomized to elinzanetant, the imputation model will have the dependent variable as the endpoint measurement at week 4 with the baseline measurement and the stratification factor, type of treatment of pre-existing condition, at baseline. The multiple imputation model will be estimated only based on placebo participants who remain in the study through week 4 and have available data at week 4. Similarly, week 1, 8 and 12 values missing after an ICE will be imputed using the same model specification but with endpoint measurement at week 1, 8 or 12, respectively, as the dependent variable.

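### Protocol 7.2 lets investigators withdraw a woman from the study for stopping endocrine therapy, although the primary estimand asks for her later data; the effect is probably small and avoidable

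*Protocol*

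**What the plan says.** **Conduct.** Protocol 7.2 covers a participant who stops tamoxifen or an aromatase inhibitor during part A+B: "the investigator will decide whether the participant should be withdrawn from the study". No criteria follow. The consequence of withdrawal is stated in the same section: "The participant will be permanently discontinued both from the study intervention and from the study at that time". End-of-treatment (EoT) and follow-up visits are requested if possible, and the section asks for no further diary data.

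**Estimand.** Protocol Table 3-2 lists "Interruption/ discontinuation in intake of adjuvant endocrine therapy", for all reasons, as an intercurrent event under treatment policy, with the instruction "Utilise the collected data after ICE". SAP Table 1-2 repeats this. SAP 4.2.1 states: "A treatment policy strategy will be applied to handle all of the ICEs in this trial in the main estimand", and adds that "all collected data should be utilized in the analysis irrespective of occurrence of the ICEs". It also expects all participants to be followed after such events, while accepting that some data may be missing. Protocol 9.4.3 applies the same strategy to the key secondary endpoints.

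**Fallback.** SAP 4.2.1 says that "the washout method will be used to impute missing data from participants who experience the ICEs", and specifies in brackets that permanent treatment discontinuation is meant. Missing placebo values are treated as missing at random.

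**The concern.** A treatment-policy estimand depends on outcomes being observed after the intercurrent event. Here one of the listed events is itself a permitted ground for ending observation. When study drug is stopped, the protocol protects follow-up: Section 7.1 asks for scheduled visits and procedures to continue if the participant agrees, and Table 2-1 says she will be encouraged to stay. No comparable text covers stopping endocrine therapy.

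The loss may be informative. Endocrine therapy causes the symptoms being measured, and Protocol 4.2 says that these symptoms impair adherence. Stopping may therefore depend on symptoms, and so on treatment arm. At stake is whether the Week 4 and Week 12 estimates use what happened to these women or a model of a different situation.

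**Working it through.** **1. Same event, two instructions**

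| Question | Conduct (Protocol 7.2) | Analysis (Protocol Table 3-2, SAP 4.2.1) |
|---|---|---|
| She stops endocrine therapy in part A+B | Investigator may end study participation | Treatment policy |
| Data afterwards | None after the EoT and follow-up visits if withdrawn | Use all that are collected |
| Follow-up expected | At discretion | Yes, for all participants |

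The event in the estimand is wider than the trigger in 7.2. For tamoxifen it is a "reduction of at least 50% of planned daily dosage taken during weeks 3 and 4 OR weeks 11 and 12 compared to baseline"; for aromatase inhibitors the threshold is 30%. The SAP adds Week 1 and Weeks 7-8. A full stop that covers the assessed weeks is a subset.

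**2. What replaces the missing values**

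- *Elinzanetant.* Washout applies because withdrawal also ends study drug. The model uses baseline and type of endocrine therapy at baseline, and is fitted to placebo women still in the study with data at that week.
- *Placebo.* Regression on baseline, the stratification factor and earlier values.
- Neither model contains endocrine therapy status after baseline.

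**3. What the other analyses add**

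- Tipping point (SAP 4.2.2.2, 6.3): shifts imputed values in the elinzanetant arm only. Placebo imputations are not varied.
- Supplementary estimands (SAP 4.2.3): the first discards data after stopping endocrine therapy and models them; the second sets change to zero. Neither recovers the observed outcome.
- Mapping rules (SAP 4.1.2): EoT values of PROMIS SD SF 8b and MENQOL can be assigned to a planned week (days 71-82 for Week 12), so some key secondary values are kept. The hot flash diary has no such rule.

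**4. The plan's own power figure**

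Inputs from Protocol Table 9-1: SD 4.29, difference -1.50, N = 243 and 122, one-sided alpha 0.025. A noncentral t calculation gives 88.16%, as stated.

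SE of the Week 12 difference = 4.29 × √(1/243 + 1/122) = 0.476, about 0.48 hot flashes/day.

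**5. Illustration of size**

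Assumed, because the documents give no figures: 2-5% stop endocrine therapy before Week 12, half of them are withdrawn, and imputed values differ from true values by 3 hot flashes/day.

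- Elinzanetant women affected: 270 × 0.02 × 0.5 = 2.7, to 270 × 0.05 × 0.5 = 6.75.
- Placebo women affected: 135 × 0.02 × 0.5 = 1.35, to 135 × 0.05 × 0.5 = 3.375.
- Shift in an arm's mean: 2.7 × 3/270 = 0.03, to 6.75 × 3/270 = 0.075. It is the same in placebo: 1.35 × 3/135 = 0.03, to 3.375 × 3/135 = 0.075.
- Relative to the SE: 0.03/0.476 = 6%, to 0.075/0.476 = 16%. Relative to a difference of 1.50: 2% to 5%.

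| Pattern | Effect on the treatment difference |
|---|---|
| Equal rates, equal errors, same sign | 0 |
| 5% stop in one arm, 2% in the other, same error | 0.075 - 0.03 = 0.045 |
| One arm only | 0.03 to 0.075 |
| Equal size, opposite signs | 0.06 to 0.15 |

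**6. Precision**

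If a further 1%, 2%, 5% or 10% of the 243/122 were simply lost, Week 12 power at -1.50 would be 87.8%, 87.5%, 86.5% or 84.6%.

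**The case against.** The best defence is that the two documents can be read together. Section 7.2 permits withdrawal but does not require it. The next line says that participants who stop in part C should be withdrawn, so the authors drew a distinction and left room to stay where efficacy is measured. Table 3-2 asks for the data that are collected, and the SAP foresees missing values and prespecifies how to fill them.

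Exposure is also limited. Entry requires endocrine therapy that is stable for at least 6 weeks and expected to continue (Protocol 5.1). Intercurrent events are flagged only to day 84, and part C has no efficacy assessments.

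Most of this stands, and it rules out three stronger readings that a reader might infer:

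- *That the protocol directs sites to discard data the estimand needs.* In part A+B it only permits it.
- *That the treatment difference is biased by a known amount or in a known direction.* The arithmetic above shows a shift in one arm. Net bias needs stopping rates or imputation errors that differ between arms, and the documents support no figure for either.
- *That washout covers every woman who stops endocrine therapy.* The SAP ties it to permanent discontinuation of study drug; it applies here only because study withdrawal ends both.

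What the defence does not answer is that the loss serves no stated purpose. Permission without criteria sits badly with an analysis that expects follow-up, and the planned imputations cannot represent women who have stopped the therapy that causes the symptoms.

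**Conclusion.** The point holds as an avoidable gap between conduct and estimand. It is confined to withdrawals before about day 84. It affects the primary endpoints and, because of the EoT mapping, the key secondary endpoints less. Neither the tipping-point analysis nor the supplementary estimands recover the missing outcomes.

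The effect is probably small. Under the assumed inputs, one arm's mean moves by 0.03-0.075 hot flashes/day against a standard error of about 0.48; the effect on the difference could be nil or, with opposite errors in the two arms, up to 0.15. These figures rest on assumed rates and an assumed error of 3 hot flashes/day. The direction is unknown. The sample size calculation is not at fault. A change is worth making because it is cheap and protects data on which the primary estimand depends.

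**What to change.** Reconcile Protocol 7.2 with Table 3-2:

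- State that, up to Visit T6, stopping adjuvant endocrine therapy is not in itself a reason for withdrawal from the study. Say that this includes its use as a compliance reason under the first bullet of 7.2; otherwise the general discretion there would bypass the change.
- State that diary and questionnaire collection continues to Week 12, whether or not study drug continues, unless the participant withdraws consent or the investigator documents a separate safety reason.
- In the SAP, add a count by arm of participants withdrawn from the study after stopping endocrine therapy before day 84.

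Decisions on endocrine therapy and study drug are not addressed here.

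The cost is a sentence or two in a protocol amendment and one table. The hot flash diary is completed at home, so the extra burden falls on few women and is slight. The SAP history already refers to review of blinded data. For participants past Week 12 an amendment recovers nothing, and the count by arm is then the useful part.
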